4.2 Exclusion Criteria

1. Patient is not a candidate for breast conservation.
2. Patient is male.
3. Age < 18 years
4. Patient requires regional lymph node irradiation therapy
5. Patient has evidence of distant metastases
6. Karnofsky Performance Status less than 80% within 60 days prior to study.
7. Ipsilateral mammogram done greater than 6 months prior to study.
8. Women of childbearing potential with a positive serum beta hCG.
9. Patient unable to consent or comply with study guidelines.
10. BMI < 21
11. Weight < 100 lbs
12. Unintentional weight loss $\geq 10\%$ in the last 3 mos

13. Prior invasive non-breast malignancy unless disease free for a minimum of 1 year prior to registration
14. Two or more breast cancers not resectable through a single lumpectomy incision
15. Non-epithelial breast malignancies such as sarcoma or lymphoma
16. Prior radiotherapy to the ipsilateral breast or prior radiation to the region of the breast that would result in overlap of radiation therapy fields
17. Severe, active co-morbidity, defined as follows:
 - Unstable angina and/or congestive heart failure requiring hospitalization within the last 6 months
 - Transmural myocardial infarction within the last 6 months
 - Acute bacterial or fungal infection requiring intravenous antibiotics at the time of registration;
 - Chronic Obstructive Pulmonary Disease exacerbation or other respiratory illness requiring hospitalization or precluding study therapy within 30 days before registration;
 - Hepatic insufficiency resulting in clinical jaundice and/or coagulation defects; note, however, that laboratory tests for liver function and coagulation parameters are not required for entry into this protocol
 - Acquired Immune Deficiency Syndrome (AIDS) or HIV positive based upon current CDC definition; note, however, that HIV testing is not required for entry into this protocol. The need to exclude patients with AIDS or HIV from this protocol is necessary because anti-retrivirals may alter patient metabolism.
18. Active systemic lupus erythematosus, or any history of active scleroderma, dermatomyositis with active rash
19. Active Gastrointestinal/Malabsorption disorder at the discretion of the Principal Investigator
 - Inflammatory Bowel Disease
 - Celiac Disease
 - Chronic Pancreatitis
 - Chronic Diarrhea or Vomiting
 - Active Eating Disorder
20. Current use of steroids
21. Active drug/alcohol dependence or abuse history.
22. Decisionally impaired patients.

4.3 Gender/Minority/Pediatric Inclusion for Research

This protocol will enroll all women with breast cancer and will include minorities in the research protocol. Pediatric patients are excluded.

4.4 Subject Recruitment and Screening

Patients who are 18 year of age or older and are candidates for breast conservation for their breast cancer are eligible for the study. Patients can be recruited from the PI, co-investigators' or referring physician's clinical practices. We have designed a brochure to try and help with patient recruitment. This brochure is attached in the Appendix VIII Section. Potential study subject should be referred to PI or study designated research nurse/research associate. Appropriate laboratory or diagnostic testing necessary to meet any noted inclusion or exclusion criteria will be ordered

through the recruiting physician. PI of the study or study designated research nurse/research associate will screen and determine the final eligibility of the subject for enrollment.

4.5 Early Withdrawal of Subjects

4.5.1 When and How to Withdraw Subjects

Patients will be informed that they have the right to withdraw from the study at any time for any reason, without prejudice to their medical care. The investigator also has the right to withdraw patients from the study for any of the following reasons:

1. Intercurrent illness
2. Occurrence of an unacceptable adverse event such as a Grade ≥ 4 toxicity or $\geq 20\%$ weight
3. Missing more than 3 consecutive days of planned radiation
4. Patient request
5. Protocol violations based on the judgment of PI
6. Non-compliance
7. Administrative reasons
8. Failure to return for follow-up
9. General or specific changes in the patient's condition unacceptable for further treatment in the judgment of the investigator
10. Patients may withdraw from the study voluntarily at any time; however, the Principal Investigator reserves the right to remove patients from the study for any of the following reasons.
11. Radiation toxicity becomes too severe and the patient can no longer tolerate consecutive radiation treatments as determined by treating radiation oncologist.
12. Patients are hospitalized for another condition that is unrelated to breast cancer. Particularly admissions lasting longer than 4 days.
13. Patients develop any of the exclusionary conditions during treatments including: hepatic insufficiency, diabetes, disorders requiring corticosteroid treatment, renal failure or pregnancy.
14. Patients become sexually active and do not wish to use contraception or patients discontinue previous method of contraception and remain sexually active.

At the time of withdrawal, all study procedures outlined for the End of Study visit should be completed. The primary reason for a patient's withdrawal from the study is to be recorded in the source documents.

4.5.2 Data Collection and Follow-up for Withdrawn Subjects

According to FDA regulations, when a subject withdraws from the study, the data collected on the subject to the point of withdrawal remains part of the study database and may not be removed.

A subject who is withdrawing needs to state whether he/she wishes to provide continued follow-up and further data collection subsequent to withdrawal from the interventional portion of the study.

If a subject withdraws from the interventional portion of the study, but agrees to continued follow-up of associated clinical outcome information as described in the previous bullet, the subject will continue follow up visit and evaluation per the protocol.

If a subject withdraws from the interventional portion of a study and does not consent to continued follow-up of associated clinical outcome information, study data related to the subject collected prior to the subject's withdrawal from the study will included in the study analysis. However, the subject's clinical data will not be used for dose escalation determination.

5 Study Drug/Therapy

5.1 Description

Baseline caloric intake will be assessed by food diaries for 7 to 10 days prior to radiation treatment planning. Recommendations by nutritional counseling will be made to decrease total caloric intake by 25% and the patient will begin this diet immediately after the planning session and for a minimum of 2 weeks before starting radiation. The patient will then remain on this calorically restricted diet as measured by food diaries until completion of radiation treatment and for a minimum of 2 weeks after the completion of the radiation course. This is done to ensure that he patients undergo caloric restriction for a minimum of 10 weeks +/-1-2 weeks.

Restriction of calories is the primary objective of dietary modification and will be tailored to each patient by the discretion of the recommending physician in Integrative Medicine to ensure overall nutrition. Diet guidelines and compliance will be reviewed at weekly on-treatment visits by study staff including physicians and diet counselors.

5.2 Treatment Regimen

5.2.1 Prior to Radiation:

Caloric restriction to 75% of normal calorie intake will begin when patients present for radiation treatment planning. Prior to this, patients will have recorded their daily intake in food journals for 2 weeks. Patients will remain on this calorically restricted diet until completion of radiation treatment for a total of 10 weeks.

Restriction of calories is the primary objective of dietary modification; however, to patients will be encouraged to maintain adequate nutrient intake. Diet guidelines and adherence will be enforced at weekly on-treatment visits by study staff including physicians and diet counselors.

5.3 Risks of Caloric Restriction

Likely (>10%)

- Weight loss
- Fatigue
- Irritability

Possible

- Decreased bone mineral density
- Decreased muscle mass and strength
- Dehydration
- Constipation
- Depression
- Fainting

Rare (<2%)

- Cholelithiasis
- Reversible amenorrhea
- Malnutrition
- Reduced sex drive
- Acidosis

5.4 Method for Assigning Subjects to Treatment Groups

As a feasibility trial, all patients will be expected to be on treatment as defined by caloric restriction, radiation therapy and nutritional counseling.

5.5 Preparation and Administration of Study Drug/Therapy

Patients will be expected to keep food diaries for 7 to 10 days prior to radiation treatment planning in order to calculate each patient's appropriate calorie intake during the treatment period. Initially, patients will have a consultation with integrative medicine and they will meet weekly with research staff for nutritional guidance and behavioral counseling to maintain their dietary modification. Patients will be expected to record their dietary intake on a daily basis while on treatment and these food journals will be collected weekly and modifications will be suggested accordingly. Patients will ultimately be responsible for modifying their diet as recommended to them.

5.6 Compliance Monitoring

Adherence to dietary modification will be monitored by self-reported calorie intake in food journals that will be collected on a weekly basis. Patients will be expected to complete food diaries accurately to represent the type and quantity of food they consumed. Patients who have internet access at home and are comfortable with computers will be given the option of using an online food diary that is password protected, but viewable by the study staff. Should patients select this option, they will be assigned a username and create their own password.

The mean weekly caloric intake will be measured and adherence will be compared with their baseline evaluation. Patients will have to maintain a weekly 25% reduction of caloric intake for 80% of the logged events in order to be considered compliant for this trial.

See Appendix IX for printed food diary and access to online food diary.

5.7 Prior and Concomitant Therapy

Patients should continue taking their daily medications on a regular basis. Patients should not be taking corticosteroids, anti-retrovirals that would exclude them from participation.

6 Study Procedures

6.1 Treatment Overview

		Wk 1	Wk 2	Wk 3-4	Wk 5-10.5	Wk 11-12
Patients post-lumpectomy	Day	All	All	All	1 2 3 4 5 6 7	All
	Diet	Normal	Normal	CR Diet	Continue CR Diet	CR Diet
	Radiation	None	Simulation	None		None

6.2 Study Visit Schedule

6.2.1 Screening

Eligibility of patients will be verified based on clinical staging and any need for adjuvant chemotherapy as well as previously stated eligibility criteria. Those eligible patients will receive detailed information about the study including a step-by-step outline of proposed treatment including radiation therapy and diet modification. Patients will be informed of possible risks and benefits. Informed consent will be obtained from patients. A full history and physical examination will be performed on consented patients. Baseline weight and BMI will be taken. In addition, blood will be drawn for eligibility measurements of beta-hCG if appropriate.

6.2.2 Phase I—Pre-treatment

Visit 1: Patients will report to the Radiation Oncology Department for radiation treatment planning to include CT simulation. Food diaries from the previous 7-10 days will be collected and analyzed to create a diet plan for each patient. Integrative medicine will meet with patients to counsel them on lifestyle changes and behavioral aspects of dietary modification. Dietary counselors will give patients guidelines for dietary modification including the appropriate amount of calories that each patient should be receiving and what kinds of foods they should avoid or eat more of. Nutritional counseling will be done using behavioral cues to encourage adherence (see Appendix V for worksheets). Patients will be instructed to begin their new diet starting at this visit and to continue logging foods into their journals. They will complete the journal daily. Patients will undergo a focused examination to assess initial breast appearance and texture for comparison as patients receive radiation therapy. Fasting blood will be drawn for baseline laboratories at this visit. Clinical measurements will include CBC w/diff, CMP, HbA1c, IGF-1, adiponectin, leptin, estradiol, triglycerides, insulin, ESR. Separately, blood samples will also be

analyzed for the following: IGF-1R, IRS-1 and other experimental endpoints such as genomic or proteomic alterations. Baseline psychosocial evaluation will be done using the FACT-B form as well as a baseline fatigue assessment using the PROMIS cancer fatigue short form (see appendix XI). Weight, height, vital signs, bioimpedance and caliper measurements will be done.

Phone Intervention: Patients will be contacted at least once a week during the time they are keeping the food journal to determine if help is needed.

Visit 2: Week 1 or day 7 (± 2 day) of diet. Weight will be measured and vital signs will be taken. Food diary from previous week to be collected, as well as 24hr recall of diet.

Visit 3: Week 2 of diet. Weight will be measured and vital signs will be taken. Food diary from previous week to be collected, as well as 24hr recall of diet.

6.2.3 Phase II—Visits During Radiation Treatment

Visit 4-9: Patients will be monitored for acute radiation toxicity including skin changes and desquamation. Patients will be questioned and examined to ensure general health and will be reassured about radiation-related side effects. Patients will turn in their food diary from the previous week and dietary counselors will review these with the patients to determine how they can continue to comply with dietary modification. At each visit, a 24hr recall of diet will be asked of the patient and compared with the diet journal to determine the self reporting accuracy. Each week during this period, patients will be counseled on their diet and given behavioral modification lessons corresponding to specific weeks in the diet (see Appendix V for worksheets). Weight will be taken at weeks 3, 5 and 7 of the diet, corresponding to weeks 1, 3 and 5 of radiation and vital signs will be performed weekly. FACT-B psychosocial assessment will be given at visit 7 along with the PROMIS cancer fatigue short form. In addition, at visit 7 (week 5 of diet) patients will have a fasting blood draw done for insulin level.

Radiation will be planned to be administered 5 days a week, Monday through Friday. Radiation is given for approximately 6-6.5 weeks or 30-33 treatments.

6.2.4 Phase III—Post Radiation Treatment

Visit 10: Week 9 of diet, for scheduling purposes. Weight and vital signs will be measured. Patients will be monitored for acute radiation toxicity including skin changes and desquamation. Patients will turn in their food diary from the previous week and dietary counselors will review these with the patients to determine how they can continue to comply with dietary modification. A 24hr recall of diet will be asked of the patient and compared with the diet journal to determine the self-reporting accuracy. Patients will be counseled on behavioral modification for the final week of their diet (see Appendix V for worksheet). Weight and vital signs will be measured.

Visit 11: Week 10 of diet, +/- 3-5 days for scheduling purposes, last day of diet; Fasting blood draw to be done for CBC, basic metabolic panel, hemoglobin A1C, triglycerides, insulin, IGF-1, erythrocyte sedimentation rate (ESR), adiponectin, leptin and estradiol. Separately, blood will be analyzed for IRS-1, IGF-1R. Weight and vital signs will be measured. Conclusion bioimpedance and caliper measurements will be taken. Patients will be monitored for acute radiation toxicity including skin changes and desquamation. Patients will turn in their food diary from the previous week and dietary counselors will review these with the patients to determine how they can continue to comply with dietary modification. A 24hr recall of diet will be asked of the patient and compared with the diet journal to determine self-reporting accuracy. Patients will complete the FACT-B psychosocial evaluation as well as the PROMIS cancer fatigue short form.

Visit 12: 4 weeks after completion of diet. Fasting blood draw to be done for CBC, basic metabolic panel, hemoglobin A1C, triglycerides, insulin, IGF-1, erythrocyte sedimentation rate (ESR), adiponectin, leptin and estradiol. Separately, blood will be analyzed for IRS-1, IGF-1R. Weight, bioimpedance, caliper measurements and vital signs will be measured. Patients will be monitored for acute radiation toxicity including skin changes and desquamation. Patients will turn in their food diary from the last diet week. FACT-B and PROMIS cancer fatigue short form will be administered.

6.3 Study Flowchart

Examination	Pre-Treatment					Radiation Treatment								Post RT		Follow-up
	Screening	Surgery	Sim	Week of Caloric Restriction Diet		3	4	5	6	7	8	9	10			
Visit Number	0	1	2	1 3 D7	2 4 D14	5	6	7	8	9	10	11	12 Las t	13		
Informed Consent	X															
Background Info (demographics, meds, medical history)	X															
Inclusion/Exclusion Criteria	X															
Vital Signs			X	X	X	X	X	X	X	X	X	X	X	X		
H&P; Performance Status	X															
Focused Physical			X			X	X	X	X	X	X			X		
Weight, BMI	X		X	X		X		X		X			X	X		
Caliper Measurements, Bioimpedance			X										X	X		

Clinical Labs: CBC w/diff, CMP, HbA1c Serum: IGF-1, adiponectin, leptin, estradiol, triglycerides, fasting insulin, ESR			X											X	X
Fasting insulin level								X							
Other Labs: IGF-1R, IRS-1, FACT-B Psychosocial Evaluation			X											X	X
PROMIS cancer fatigue short form			X					X						X	X
Specimen sent to Pathology for histologic exam andER, PR, HER2		X													
Dietary Counseling	X		X			X	X	X	X	X	X				
Behavioral Counseling				X		X	X	X	X	X	X	X			
Food Diary Collected			X	X	X	X	X	X	X	X	X	X	X	X	
Acute Toxicity Assessment			X			X	X	X	X	X	X	X	X	X	X

Key: H&P=Full history and physical exam
 Sim=Radiation simulation planning session
 RT=Radiation Therapy
 D7=Day 7 of caloric restriction diet; D14=Day 14 of caloric restriction diet
 Last=Final day of caloric restriction diet

6.4 Radiation Treatment

6.4.1 Dose Specifications

6.4.1.1 Breast: 50 Gy in 25 fractions of 2 Gy.

6.4.1.2 Lumpectomy PTV Cavity: Total dose will be 10-16 Gy in 5-8 fractions

6.4.1.3 Total radiation dose 60-66Gy

6.4.2 Technical Factors

6.4.2.1 The patient may be treated by photon or electron radiation therapy. Fields and treatment type will be up to the discretion of the treating radiation oncologist and may include but is not limited to 3D-RT, IMRT and en face.

- 6.4.2.2 The guidelines for IMRT in this trial will conform to the policies set by the Advanced Technology Consortium (ATC) and the National Cancer Institute (NCI) http://atc.wustl.edu/home/NCI/NCI_IMRT_Guidelines.html
- 6.4.2.3 Megavoltage photon beams with energies ≥ 6 MV and megavoltage electron beams are required.

6.4.3 Localization, Simulation, and Immobilization

- 6.4.3.1 Simulation and treatment may be performed with the patient in the supine or prone position.
- 6.4.3.2 Patients should be optimally positioned with immobilization devices at the discretion of the treating physician such as alpha cradle casts, breast boards, wing boards.
- 6.4.3.3 Methods to minimize the cardiac exposure to RT like heart block, gating or breathhold are allowed at the discretion of the treating physician
- 6.4.3.4 For large-breasted patients, including those with a large inframammary skin fold, devices to improve positioning of the breast are permissible.
- 6.4.3.5 A treatment planning CT scan in the treatment position will be required to define the tumor bed for boost.
 - 6.4.3.5.1 The CT required for generation of a virtual plan with 3DCRT or IMRT must be post-lumpectomy
 - 6.4.3.5.2 Radio-opaque markers must be placed on external landmarks at the acquisition of the CT scan to facilitate contouring segmentation of the CT data-set. These markers should identify: 1) The lumpectomy incision 2) Additional markers to define the clinical borders of tangent fields (e.g. based on the palpable breast tissue and boney landmarks).
 - 6.4.3.5.3 The CT should extend cephalad to start at or above the mandible and extend sufficiently caudally (or inferiorly) to the inframammary fold to encompass the entire lung volume. A CT scan image thickness of ≤ 0.5 cm should be employed.
 - 6.4.3.5.4 External skin localizing marks, which may include permanent tattoos, are recommended for radiation daily localization and set-up accuracy.

6.4.4 Treatment Planning/Target Volumes

- 6.4.4.1 Planning isodose lines will be chosen by treating physician.
- 6.4.4.2 Target Volumes and Normal Structures
- 6.4.4.3 Lumpectomy CTV: Contour using all available clinical and radiographic information including the excision cavity volume, architectural distortion, lumpectomy scar, seroma and/or extent of surgical clips (clips are strongly recommended). Patients without a clearly identifiable lumpectomy bed do not need a boost. Lumpectomy CTV volume will be expanded by 1.5 to 2cm at the physicians discretion and the expanded volume (Lumpectomy PTV) will be treated.
- 6.4.4.4 Ipsilateral lung. This may be contoured with auto-segmentation with manual

verification.

- 6.4.4.5 Contralateral lung. This may be contoured with auto-segmentation with manual verification
- 6.4.4.6 Heart: The heart should be contoured beginning just inferior to the level in which the pulmonary trunk branches into the left and right pulmonary arteries (PA). Above the PA, none of the hearts 4 chambers are present. All the mediastinal tissue below this level should be contoured, including the great vessels (ascending and descending aorta, inferior vena cava). The heart should be contoured on every contiguous slice thereafter to its inferiormost extent near the diaphragm. If one can identify the esophagus, this structure should be excluded from the heart. One need not include pericardial fat, if present. Contouring along the pericardium itself, when visible, is appropriate.

6.5 Treatment Verification

6.5.1 Before first treatment:

Portal films or images of each 3DCRT beam and an orthogonal pair for all patients must be obtained and approved by a physician prior to initiation of treatment.

6.5.2 Subsequent images or films:

Subsequent treatment images may be obtained every fraction. At the minimum, orthogonal pair films or treatment images must be obtained prior to fraction number 5 and every 5 fractions subsequently. The imaging modality and process should be performed based on the institutional guidelines.

6.6 Radiation Therapy Adverse Events

All Radiation Therapy AEs will be scored according to the NCI Common Terminology Criteria for Adverse Events (CTCAE) version 4

Short Term: Fatigue is an anticipated systemic reaction to radiation treatment. Skin erythema, desquamation, breast edema, breast tenderness and myositis are potential local reactions.

Long Term: Long term effects possibly include radiation pneumonitis, rib fractures, second malignancy and for left-sided lesions cardiac complications

7 STATISTICAL PLAN

7.1 Sample Size Determination

The study will enroll a total of 90 patients. For Phase 1, with a sample size of 40, the study has 83% power to establish that adherence is higher than 60%, assuming that true adherence will be 80% or greater (one-sided exact binomial test with alpha 0.05).

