7.2 Statistical Methods

Primary endpoint (adherence). We will compute the proportion of patients who are adherent to the diet restriction (as defined in section 3.2), along with a 95% exact confidence interval. We will also use an exact binomial test (with a one-sided alpha of 0.05) to test whether adherence is greater than 60%.

Aim 1b. We will compute the proportion of patients with toxicity, along with a 95% exact confidence interval. Our institution's historical toxicity rate among similar patients is about 80% and we aim to prove that the dietary intervention is non-inferior with an absolute margin of 10%, using an exact binomial test. With a total sample size of 90 and assuming that true toxicity will be 80% or lower, we have 82% power (with one-sided alpha of 0.05).

Secondary endpoints. The change in body fat measurement between baseline and the end of the study will be analyzed via a paired t-test. Weight changes over time will be assessed by modeling BMI as a function of time (baseline, diet weeks 1, 3, 5, 7, and 10) via mixed-effects regression. The patterns of change over time in vital signs, insulin and other clinical labs, serum markers, and psycho-social outcomes (FACT-B) will also be analyzed similarly. If some of these measures are skewed, we will transform them (e.g., log) before the analyses. Finally, local recurrence, distant metastases, progression free survival, and overall survival will be analyzed via survival methods, specifically the Kaplan-Meier method and the logrank test. If sufficient events occur, we may assess the impact of various patient and clinical/treatment variables on these outcomes via Cox proportional hazards regression.

Local recurrence, progression free survival, distant metastases and overall survival will be assessed and compared with historic controls using the Kaplan Meier method. Local recurrence, progression free survival, distant metastases and overall survival will be measured from the date of study enrollment to time of event.

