7.3 Subject Population(s) for Analysis

All subjects enrolled in the study who completed at least 4 food diaries per week during the diet modification phase will be used for analysis.

8 Safety and Adverse Events

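### The stated powers of 83% and 82% hold only if all 40 and all 90 enrolled patients are analysed, yet Section 7.3 restricts the analysis to diary completers and no allowance is made

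*Combined protocol and SAP*

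**What the plan says.** - **Adherence (Study Summary, 7.1, 7.2).** The plan states that "with a sample size of 40, the study has 83% power to establish that adherence is higher than 60" per cent. The true rate is taken as at least 80%, and the test is exact, one-sided, at the 5% level. Section 7.2 repeats this test and refers to Section 3.2 for the definition of an adherent patient.
- **Toxicity, Aim 1b (Study Summary, 7.2).** The historical rate is put at about 80%, and the diet is to be shown no worse within 10 percentage points, again by an exact test. For power, Section 7.2 states: "With a total sample size of 90 and assuming that true toxicity will be 80% or lower, we have 82% power". The level is 5%, one-sided.
- **Enrolment.** The Study Summary enrols 40 patients in Phase 1 and 50 more in Phase 2, 90 in total. The enrolment targets therefore equal the numbers used for power. No drop-out rate, non-evaluable rate or inflation is given.
- **Analysis population (7.3).** Enrolled subjects "who completed at least 4 food diaries per week during the diet modification phase will be used for analysis". The rule is not tied to one endpoint.
- **Low-diary weeks (3.2).** A week with fewer than four diaries counts as non-adherent. The diet phase lasts at least 10 weeks.
- **Withdrawn patients (4.5.2).** Data collected before withdrawal stay in the analysis, and patients who agree to it continue their follow-up visits.

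**The concern.** The power statements use the number enrolled, while the population rule describes a set that can only be that size or smaller. Read literally, a single week with three diaries removes a patient from every analysis, including the toxicity test, although diary keeping has no bearing on whether a skin reaction can be graded. The plan therefore needs complete evaluability to deliver its stated power, and the same plan contains a rule that works against it.

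These two powers are the only justification given for the sample size. If non-inferiority on toxicity were not shown, a reader would credit the test with 82% power when the analysed set might have had less. There is also a selection problem: removing poor diary keepers would probably raise the observed adherence rate.

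**Working it through.** **Inputs.** Adherence: null 0.60, alternative 0.80, n = 40 (7.1, 7.2). Toxicity: the historical rate of 0.80 plus the margin of 0.10 gives a null of 0.90; the assumed true rate is 0.80 and n = 90 (7.2). Both tests are exact binomial, one-sided, alpha 0.05.

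**Method.** For adherence, take the smallest r with P(X ≥ r | n, 0.60) ≤ 0.05; power is P(X ≥ r | n, 0.80). For toxicity, take the largest c with P(X ≤ c | n, 0.90) ≤ 0.05; power is P(X ≤ c | n, 0.80). The critical value is derived afresh for each n.

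**Step 1: the plan's own figures.**
- n = 40: reject at 30 or more adherent; exact alpha 0.0352; power 83.9% (stated 83%).
- n = 90: reject at 75 or fewer with toxicity; exact alpha 0.0333; power 82.1% (stated 82%).

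Both are reproduced.

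**Step 2: smaller analysed numbers.**

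| Adherence n | Power | Toxicity n | Power |
|---|---|---|---|
| 40 | 83.9% | 90 | 82.1% |
| 39 | 85.9% | 89 | 80.7% |
| 38 | 78.4% | 88 | 79.3% |
| 37 | 80.9% | 87 | 77.8% |
| 36 | 83.2% | 86 | 84.1% |
| 35 | 74.5% | 85 | 82.8% |
| 34 | 77.3% | 80 | 75.3% |
| 33 | 80.0% | 79 | 82.2% |
| 32 | 69.8% | 78 | 80.8% |

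Power moves in a saw-tooth because the critical value is a whole number. Losing 1 or 4 of 40, or 4, 5 or 11 of 90, keeps at least the stated power. Losing 2 or 3 of 40, or 1 to 3 or 6 to 10 of 90, does not. Once 5 or more of 40 are excluded (computed from 35 down to 28), or 12 or more of 90 (from 78 down to 65), power is below the stated figure at every n.

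**Step 3: averaging over the saw-tooth.** Let each patient be excluded independently with probability d, unrelated to outcome, so that the analysed number M is Binomial(N, 1 − d). Average power is the sum over m of P(M = m) × power(m). The values of d are assumptions.

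| Assumed exclusion | Adherence (N = 40) | Toxicity (N = 90) |
|---|---|---|
| 5% | 81.9% | 80.9% |
| 10% | 79.5% | 79.2% |
| 15% | 77.0% | 77.3% |
| 20% | 74.1% | 74.7% |

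Shortfall at 10%: 83 − 79.5 = 3.5 points and 82 − 79.2 = 2.8 points. At 20%: 83 − 74.1 = 8.9 and 82 − 74.7 = 7.3.

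**Step 4: the population rules side by side.** If a logged event is a week, 3.2 asks for 0.80 × 10 = 8 adherent weeks in a 10-week diet. A patient with one or two low-diary weeks can then still be adherent under 3.2, while 7.3 read literally drops her. The two sections give different denominators for the same endpoint. For toxicity, 3.2 is silent because it scores diet weeks, and 7.3 is the only population named.

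**The case against.** Several points on the other side are sound.

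- **There is no calculation error.** The powers are stated conditionally on 40 and 90 and are right for those numbers. A reader might infer that they were miscalculated; Step 1 shows otherwise. What is missing is an allowance.
- **Small losses need not matter.** A reader might infer that losing any few patients takes power below the stated figure. The exact results do not support that: 39 of 40 gives 85.9% and 86 of 90 gives 84.1%. At an assumed 5% exclusion the average shortfall is only about 1 point for each test.
- **Section 3.2 may protect the adherence test.** If 3.2 governs, poor diary keepers stay in the denominator, n stays at 40 and power stays at 83.9%, provided the assumed 80% already counts such patients as failures. This stands as a reading, but 7.3 contradicts it and the plan does not say which prevails. It does nothing for toxicity.
- **Withdrawal does not by itself shrink the analysed set.** The withdrawal list in 4.5.1 might look like a further source of lost patients. Section 4.5.2 keeps their earlier data in the analysis, so the list does not support that inference. But 4.5.2 also sits awkwardly with the diary requirement in 7.3.
- **The size is assumed.** No exclusion rate is given, and a shortfall of about 3 points at 10% is modest for a single-arm pilot. This is accepted.

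**Conclusion.** The point holds in limited form. The powers of 83% and 82% are correct only with all 40 and all 90 patients analysed; 7.3 does not preserve those numbers, and no allowance is stated. The effect is about 1 point at 5% exclusion, about 3 points at 10%, and about 7 to 9 points at 20%. These sizes rest on assumed rates, on exclusion unrelated to outcome, and on true rates staying at 80%.

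The case is firmest for toxicity. For adherence, the more certain defect is that 3.2 and 7.3 disagree on who is counted. It would go too far to read a negative adherence result as a consequence of low power: dropping poor diary keepers would probably push the observed rate up, so bias may matter more there than lost patients.

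**What to change.** Replace 7.3 with one population per test:

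- **Adherence:** all enrolled patients, with weeks of fewer than four diaries scored non-adherent as in 3.2.
- **Toxicity:** all patients who received radiation, whatever their diary completion.

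This keeps the analysed numbers at or near the 40 and 90 behind the stated powers, removes selection on diary keeping, and brings 7.3 into line with 3.2 and 4.5.2. It changes the analysis population but adds no patients. The price is that the observed adherence rate may be lower. The 83% then requires 80% to be the rate among all enrolled, and the plan should say so: if 4 of 40 were certain failures and the other 36 each had an 80% chance, the power to reach 30 would be 40.1%.

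If 7.3 is kept, state in the Study Summary, 7.1 and 7.2 that 83% and 82% apply only at 40 and 90 evaluable patients, and give about 79% for each test at an assumed 10% exclusion. This costs wording and a slightly less favourable stated power. Sections 3.2, 4.5.2 and 7.3 would still need to be reconciled.
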